7.1 Study Intervention/Patient scans

Protocol initiation quality assurance

Patient scans will be acquired on one of the Siemens Biograph mCT™ PET/CT scanners with a preference for the same instrument on all scans. Quality assurance images from each system will be acquired at the beginning of the protocol on all mCT scanners using a ^{68}Ga -filled 20-cm-diameter cylindrical water phantom with average SUVs in the range $1.0 \pm 0.5 \text{ g/ml}$ with no artifacts on visual inspection.

Individual patients preferably use the same scanner system for both scans.

Prior to imaging evaluation, patients will be permitted to eat a light meal.

An intravenous catheter (Hep-Lock) will be placed in the CBIC or WCINYP for radiopharmaceutical administration, scans, and blood sampling.

Patient scans

Two dynamic whole body ^{68}Ga -PSMA PET/CT scans will be performed successively at least 6 hours apart. As there will be an accumulation of activity in the urinary bladder, patients will have pre-treatment hydration and encourage voiding immediately prior to imaging, however the short half-life of ^{68}Ga should not result in imaging counts from the first scan to appear on the latter scan.

PET/CT imaging patients will be positioned on a flat couch in radiation treatment position. Custom-made immobilization devices, skin markings, PET/CT gantry, and room lasers will be used to ensure accurate and reproducible positioning. Imaging will start with low-dose CT scan (80 mA) for attenuation correction, followed by a PET scan. A low dose CT scan (80 mA) will be performed over the prostate or a pre-determined index lesion. A 10min dynamic PET scan at the pelvic bed position, centered over the prostate tissues, will be initiated concurrently with an intravenous bolus injection of approximately 2.5MBq/kg of body weight ($\pm 10\%$) of ^{68}Ga -PSMA, followed by a time series of whole-body PET scans (passes) at least 10-75 min and at most 10-90 min post injection. The PET acquisition time per bed position per pass will be fixed at 30sec and the total number of passes summed post acquisition to produce the static ^{68}Ga -PSMA PET images will be at least six. The total number of late passes may be increased, if needed, such that the product of total acquisition time per bed position from all passes and injected activity is at least 7.5 MBq/kg*min or a total acquisition time of 90min is reached.

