11.2.5 Record Retention

Essential documents are those documents that individually and collectively permit evaluation of the study and quality of the data produced. After completion of the study, all documents and data relating to the study will be kept in an orderly manner by the Investigator in a secure study file. Essential documents should be retained for 2 years after the final marketing approval in an ICH region or for at least 2 years since the discontinuation of clinical development of the IP. In addition, all subjects medical records and other source documentation will be kept for the maximum time permitted by the hospital, institution, or medical practice.

12. Statistical Considerations

Up to 30 patients will undergo a dynamic whole-body scan with ^{68}Ga -PSMA_{Gen} and later ^{68}Ga -PSMA_{cyc} with a maximum time of 2 days and a minimum time of 6 h between the two injections. All 22 patients will receive ^{68}Ga -PSMA_{Gen} at a specific activity of 1-2 Ci/ μmol , the typical specific activity used in clinical trials with ^{68}Ga -PSMA. We expect the ^{68}Ga -PSMA_{cyc} to be delivered and injected at a specific activity of 0.1- 2.0 Ci/ μmol given the rigors of delivery. We will accept doses in this range as the prior small animal imaging was designed to understand the affect of specific activity over a 20X range.

For a power of 80% a calculation of the sample size needed to test odds ratio (equality test) was performed. A sample size of 22 would give a power percentage of 18.47 with a type 1 error of 5%. This power percentage is sufficient in providing confidence that the findings will reflect a true effect. The median statistical power of studies in the neurosciences is between ~8% and ~31%. We will not and should not be focusing on p-values but rather the estimates of the effect size with its confidence intervals.

Estimating repeatabilities using a mixed effects model framework has proven to be powerful, the repeatability (r) is calculated as the variance among group means (group-level variance) over the sum of group-level and data-level (residual) variance (v). A Pearson's correlation coefficient will demonstrate also present the repeatability of results. Intraclass correlation values for both groups will be calculated to test if the groups differ in repeatability. These collection of tests(functions) for estimating repeatability of measurements with a single grouping factor are all performed in R statistical software.

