To quantify the agreement between the two scans, we will use the repeated measures correlation coefficient to account for multiple observations per subject. We will calculate the repeated measures correlation-coefficient for the SUVmax and SUVmean for reference regions as well as regions suspicious for metastatic disease. We will measure SUVmean and SUVmax of the same Regions of Interest (ROI) in both scans using the PET analysis software we use in our clinical practice. The two scans will be retrieved and the exact same ROIs will be drawn at the same time for the two scans (software offers a copy-paste function so that no discrepancies exist between the two measurements). The SUVmean and SUVmax obtained from both scans for each Region of Interest will then be analyzed to determine the within-subject coefficient of variation value as measured by the Bland Altman analysis. If the agreement between the two scans lies within an acceptable rate (which we consider 30% based on previously published data), we will consider the two methods equivalent.

Also, as aforementioned the Bland-Altman Test presents proof of repeatability analysis.

13. Adverse Event Reporting Requirements

Adverse event (AE) monitoring and reporting is a routine part of every clinical trial. The investigator will be required to provide appropriate information concerning any findings that suggest significant hazards, contraindications, side effects, or precautions pertinent to the safe use of the drug or device under investigation. Safety will be monitored by evaluation of adverse events reported by subjects or observed by investigators or research staff, as well as by other investigations such as clinical laboratory tests, x-rays, electrocardiographs, etc.

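### The ±50% phantom tolerance does not protect the 30% equivalence limit when a patient's two scans are on different scanners

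*Combined protocol and SAP*

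**What the plan says.** Section 7.1 sets the scanner check: "Quality assurance images from each system will be acquired at the beginning of the protocol on all mCT scanners", using a ⁶⁸Ga-filled "cylindrical water phantom with average SUVs in the range" 1.0 ± 0.5 g/ml and free of visible artifacts. A system reading anywhere from 0.5 to 1.5 passes. The paragraph concerns protocol initiation; nothing is said about repeating the phantom.

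Scanner choice is addressed twice in the same section, each time as a preference. Across the study, scans are made "with a preference for the same instrument on all scans". For each patient, "Individual patients preferably use the same scanner system for both scans". More than one system is foreseen, and Section 2.5.1 delivers doses to either of two imaging locations.

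The primary comparison, in the Endpoints part of Section 1 and in Section 12, pairs SUVmean and SUVmax from the two scans to "determine the within-subject coefficient of variation value as measured by the Bland Altman analysis". The decision rule in Section 12 reads: "If the agreement between the two scans lies within an acceptable rate (which we consider 30% based on previously published data"; if so, the methods are considered equivalent. The documents describe no cross-calibration between scanners, no correction by the phantom reading, no scanner term in the analysis and no rule for a pair split across two scanners.

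**The concern.** Section 3.3 defines SUV as measured activity per gram of tissue over injected activity per gram of body mass. A scanner that reads high or low by some factor multiplies every SUV it produces by that factor. Copying the same regions of interest onto both scans and blinding the reader do not remove it.

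When a patient's two scans come from different systems, the ratio of the two calibration factors enters the paired difference together with any effect of production method. A check that accepts ±50% cannot keep that contribution below a 30% limit. At stake is the primary conclusion: two identical products could be declared non-equivalent because of where patients were scanned.

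**Working it through.** The plan gives no figure of its own for scanner contribution, so there is none to reproduce.

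**Inputs**
- Phantom acceptance range: 0.5 to 1.5 g/ml (Section 7.1).
- Limit: 30%, read as a limit on wCV because that is the statistic named just before the rule (Section 12).
- Number of patients: 22 and up to 30, both from Section 12.
- Assumptions: the phantom reading acts as a multiplicative calibration factor on SUV; true uptake is identical on both scans; there is no other variation unless stated.
- Not given in the documents: actual scanner readings, and the share *f* of patients who change scanner.

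**Step 1: one pair on scanners reading a and b**

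Pair wCV = |a − b| / (√2 × mean of a and b).
- 0.5 and 1.5: 1.0 / (1.414 × 1.0) = 70.7%. The ratio is 3 and the difference is 100% of the mean.
- 0.7 and 1.3: 0.6 / 1.414 = 42.4%.
- 1.0 and 0.5: 0.5 / (1.414 × 0.75) = 47.1%.
- 1.0 and 1.5: 0.5 / (1.414 × 1.25) = 28.3%.
- Same stable scanner (a = b): 0%.

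**Step 2: from the pair to the study**

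The rule is applied to a wCV over all patients. Those who stay on one scanner contribute nothing from calibration, so study wCV = pair wCV × √f. The limit is reached at f = (0.30 / pair wCV)².
- 0.5 and 1.5: f = 0.09 / 0.50 = 18%. With 22 patients, 3 changes give 70.7% × √(3/22) = 26.1% and 4 give 30.2%. With 30 patients, 5 give 28.9% and 6 give 31.6%.
- 0.7 and 1.3: f = 0.09 / 0.18 = 50%. At 11 of 22 or 15 of 30 the wCV is exactly 30.0%, so just over half must change.
- 1.0 and 1.5: 28.3% even if every patient changes, so calibration alone does not exceed the limit.

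**Step 3: allowing for other within-patient variation**

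The documents give no value. With an assumed background wCV *w* and variances that add, the share needed at the extremes is (0.09 − w²) / 0.50:

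| Assumed background wCV | Share of patients who must change |
|---|---|
| 5% | 17.5% |
| 10% | 16% |
| 15% | 13.5% |
| 20% | 10% |

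**Step 4: what a tighter tolerance would do**

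For a symmetric tolerance ±t the worst pair wCV is 2t/√2 = √2 × t. At ±10% this is 14.1%, and at ±5% it is 7.1%. Since √f cannot exceed 1, these also cap the study-level calibration contribution.

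**The case against.** The strongest reply is that the plan already points the right way. The same scanner is preferred twice, and if that is followed the calibration factor cancels whatever the phantom reads. No scanner reading or rate of change is given, so the 71% is a bound on what the rules permit, not an estimate. This stands, and it limits the point to cross-scanner pairs. It does not close it, because a preference sets no rule for the pairs that do cross.

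A reader might infer four stronger things that the documents do not support:
- **That a tolerance of only ±21% would use up the whole limit.** Solving √2 × t = 0.30 does give t = 0.212, but at study level this needs every patient to change scanner between systems at opposite edges of the range.
- **That scanner error would hide a real difference.** Calibration error unrelated to product inflates the wCV and pushes towards failing equivalence. Masking needs scanner assignment to follow production method, with an error that offsets the product effect. Section 7.11 says cyclotron shipments always come in the afternoon, so slot and product are linked, but nothing says that scanner follows slot.
- **That quality assurance is done only once.** Section 7.1 describes the check at initiation and is silent on later ones.
- **That ±0.5 is simply an error.** No passage ties the phantom range to the 30% limit, and the figure should be confirmed before it is called a mistake.

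The 30% rule is also loosely worded. Read as a percent difference within a pair, the worst case is 100% of the mean, so the tolerance is still wider than the limit.

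**Conclusion.** The point holds in limited form. As printed, the phantom tolerance is too wide to protect the primary endpoint for any patient scanned on two systems, and the plan neither forbids such pairs nor says how to handle them. Whether this could decide the trial depends on two unknowns: how far apart the scanners read, and how many patients change. At the extremes of the accepted range, just under a fifth of patients suffices; at 0.7 and 1.3 it takes just over half; at 1.0 and 1.5 calibration alone does not reach the limit.

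The likely direction of harm is a false finding of non-equivalence. The arithmetic is secure under a multiplicative calibration error; the practical impact cannot be judged from the documents. This is a cheap improvement to the plan, not a flaw that invalidates the design.

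**What to change.** - Require both scans of a patient to be on the same scanner. With stable calibration this alone removes the contribution.
- Record scanner ID for each scan.
- If a cross-scanner pair is unavoidable, keep it identifiable and report the wCV with and without such pairs.
- Confirm that ± 0.5 g/ml is intended, and tighten the acceptance range to well inside 30%. ±10% is offered as an example, not as a figure from the documents.
- Repeat the already planned phantom check at intervals over the 2-year study. The same-scanner rule relies on stable calibration, and the tighter range matters for any pair that still crosses.

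The cost is protocol wording, some repeat phantom scans and a scheduling constraint. The constraint is real: there are two imaging locations, the generator dose has a 2 h expiration (Section 2.5.1), and the cyclotron product arrives only in the afternoon (Section 7.11). A few pairs may be set aside in the sensitivity analysis, which matters somewhat with 22 to 30 patients.

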PI	Principal Investigator
REDCap	Research Electronic Data Capture
SAE	Serious Adverse Event
SUSAR	Suspected Unexpected Serious Adverse Reaction
UIRTSO	Unanticipated Problem Involving Risks to Subjects or Others
WCM	Weill Cornell Medicine
WCINYP	Weill Cornell Imaging NewYork Presbyterian
PCa	Prostate Adenocarcinoma
⁶⁸Ga	Gallium-68
PET	Positron Emission Tomography
ROI	Regions of Interest
PSMA	Prostate Specific Membrane Antigen
Ga-PSMAcyc	Ga-PSMA cyclotron
Ga-PSMAGen	Ga-PSMA generator

1. Protocol Summary

[figure not shown]
Full Title:	Evaluation of a ⁶⁸ Ga Small Molecule PSMA Antagonist Produced by two different Methods
Clinical Phase:	I/II
Principal Investigator:	[name]
Study Description:	Patients with metastatic prostate cancer will undergo two protocol ⁶⁸ Ga-PET scans within 24-48h with ⁶⁸ Ga-PSMA-cyclotron and ⁶⁸ Ga-PSMA-generator radiotracers. The goal of the study is to evaluate repeatability and equivalence across the different ⁶⁸ Ga-PSMA production methods.
Sample Size:	Up to 30 patients will be enrolled in the study as defined by protocol criteria.
Enrollment:	30 patients will be enrolled in this study
Study Population:	Patients with metastatic prostate adenocarcinoma
Enrollment Period:	2 years
Study Design:	Single-dose, non-randomized design. Patients with metastatic prostate adenocarcinoma will be administered a single intravenous dose of each of the study drugs ⁶⁸ Ga-PSMA-cyclotron and ⁶⁸ Ga-PSMA-generator 24-48 hours apart.
Description of Sites/ Facilities Enrolling	
Participants:	This is a single site study. All study procedures will be performed in the NYP/WCMC facilities, CBIC, and WCINYP.
Study Duration:	2 years
Participant Duration:	3 Visits: 1 screening/consent and 2-infusions imaging. The duration of patient participation can be up to 4 weeks, depending on eligibility, and the scheduling and completion of required study visits
Study Agent/Device Name	
Intervention Description:	⁶⁸ Ga-PSMA-cyclotron and ⁶⁸ Ga-PSMA-generator; single dose each, approximately 100-300 mBq.
Primary Objective:	
• To evaluate equivalence of two processes to create ⁶⁸Ga-HBED-PSMA (⁶⁸Ga-PSMA-cyclotron vs. ⁶⁸Ga-PSMA-generator)
Secondary Objectives:	
• Comparative dosimetry and biodistribution (⁶⁸Ga-PSMA-cyclotron vs. ⁶⁸Ga-PSMA-generator), whole body excretion/ metabolism in patients with confirmed metastatic PCa

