Exploratory Objectives:	
• Investigate repeatability of whole-body ⁶⁸Ga-PSMA-generator Ki Patlak imaging against that of conventional whole-body ⁶⁸Ga-PSMA- SUV imaging in patients with confirmed metastatic prostate adenocarcinoma.

- Evaluate equivalence of whole-body ⁶⁸Ga-PSMA Ki Patlak imaging between the two processes to create ⁶⁸Ga-HBED-PSMA (⁶⁸GA-PSMA-cyclotron vs. ⁶⁸Ga-PSMA-generator)

Endpoints:

The primary endpoint of this study is to prove equivalence between the cyclotron and generator produced radioisotope. To meet this endpoint we will make a direct comparison of the ⁶⁸GA-PSMA-cyclotron vs. ⁶⁸Ga-PSMA-generator scans obtained within 24-48h. We will measure SUVmean and SUVmax of the same Regions of Interest (ROI) in both scans using the PET analysis software we use in our clinical practice. The two scans will be retrieved and the exact same ROIs will be drawn at the same time for the two scans (software offers a copy-paste function so that no discrepancies exist between the two measurements). The SUVmean and SUVmax obtained from both scans for each Region of Interest will then be analyzed to determine the within-subject coefficient of variation value as measured by the Bland Altman analysis.

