3.1 Overall Design

Thirty patients with metastatic prostate cancer that have undergone standard-of-care staging at WCMC will be considered for enrollment. For this study, enrolled patients will undergo a total of two whole-body dynamic ^{68}Ga -PET scan protocols of at least 0-75 min and at most 0-90 min scan time post injection, depending on the amount of injected dosage. A 6 to 48 hour gap will be introduced between the two scans. The first scan will occur after a baseline clinical evaluation, which will include a history, physical, and baseline lab draw. Blood work will be obtained before, during and after the scan. The radiotracers will be evaluated for repeatability and equivalence across the different production methods. This will include basic pharmacokinetics, distribution, metabolism and excretion.

Up to 30 patients will undergo each two whole-body dynamic scans, initially with ^{68}Ga -PSMAcyc and later with ^{68}Ga -PSMagen (with a minimum time of 6 h and maximum time of 2 days between the two injections). All patients will receive ^{68}Ga -PSMagen from the CBIC core and ^{68}Ga -PSMAcyc from NCM pharmaceuticals at a specific activity of 1-2 Ci/ μmol , the typical specific activity used in published clinical trials with ^{68}Ga -PSMA (10).

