3.3 Justification for Dose

Patients will be injected with 100-300 MBq of ^{68}Ga -HBED-PSMA (from either the generator or cyclotron source) via a catheter. ^{68}Ga -PSMA PET/CT will be acquired using a Siemens Biograph mCT™ PET/CT scanner. Please see details in section 7.1.

The goal is to administer this amount of the imaging probe labeled with 2.5 MBq of ^{68}Ga per kg body weight with a minimum of 100 MBq and maximum of 300 MBq ^{68}Ga per patient.

The whole-body dynamic ^{68}Ga -PSMA scans will involve an initial dynamic scan at a pelvic scanner bed position centered over the prostate tissues for the first 10min post injection (p.i.), followed by multiple successive whole-body scans (passes) at least 10-75 min and at most 10-90 min post injection, depending on the amount of injected dosage. A fixed scan time of 30sec per bed position per pass will be used with an adjustable total number of passes. The PET data collected from at least the last six passes will be summed at each bed position and combined over all bed positions to produce whole-body static ^{68}Ga -PSMA images equivalent of a total acquisition time of $6 \times 30 \text{ sec} = 180\text{sec}$ or 3 min/bed position from all summed passes.

Due to the short physical half-life of ^{68}Ga and the decreasing elution efficiency of the $^{68}\text{Ge}/^{68}\text{Ga}$ generator during its lifetime, the amount of radioactivity injected per patient will necessarily vary. If the amount of activity per kg body weight differs by more than 25% from the recommended dose of 2.5MBq/kg of body weight, the effective total acquisition time per bed position from all passes will be adjusted by increasing the total number of passes, in increments of one pass, while keeping fixed the scan time per bed per pass. The adjustment of the total number of passes will result in the respective adjustment of the total scan time up to 90 min post injection. The total number of passes will be adjusted such that the product of total acquisition time per bed position from all summed passes participating in the synthesis of the equivalent static PET images and of the injected activity is at least 7.5 MBq/kg*min or the total scan time reached 90 min.

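### The minimum gap between the two scans is 24 h in some sections and 6 h in others; at 6 h a small residual from the first dose can reach the second scan

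*Combined protocol and SAP*

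**What the plan says.** Three places set a 24 h minimum. The Protocol Summary (Study Design) has the two doses given "24-48 hours apart". The footnote to the schedule in section 6.1 requires at least 24 h and at most 48 h. The last paragraph of section 7.1 has the patient return after 24 to 48 h. The schedule puts the scans on separate days (D1 and D2), and the Protocol Summary counts "3 Visits: 1 screening/consent and 2-infusions imaging". The Endpoints text is looser, referring to "scans obtained within 24-48h", but points to the same window.

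Four places set a 6 h minimum. Section 3.1 does so twice: "A 6 to 48 hour gap will be introduced between the two scans", and then "with a minimum time of 6 h and maximum time of 2 days between the two injections". Section 6.1.2.1 asks for at least 6 h, and in the Patient scans paragraph of section 7.1 the scans "will be performed successively at least 6 hours apart. As there will be an accumulation of activity in the urinary bladder". Section 12 repeats 6 h as the minimum and 2 days as the maximum between injections.

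On carry-over, section 7.1 says that the short half-life "should not result in imaging counts from the first scan to appear on the latter scan". It gives no half-life and no residual calculation.

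**The concern.** Both figures are stated as minimums, so they are not nested limits that can hold together, and section 7.1 contradicts itself. A pair scanned at, say, 8 h complies with section 12 and is a deviation under section 6.1. The plan does not say which rule governs or how such a pair enters the primary analysis.

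The choice also affects the measurement. The primary comparison is of SUVmean and SUVmax between the two scans. Activity left from the first injection adds counts to the second scan and never to the first. Section 7.11 rules out randomising the order, so the addition would fall on one product and would not average out over patients. Blinding the reader does not remove it. Which product is affected is itself unclear, because section 3.1 puts the cyclotron product first and section 12 the generator product.

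**Working it through.** The plan gives no residual figure to reproduce. The check sets the texts side by side and then works out physical decay.

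**Texts**

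| Place | Minimum | Maximum |
|---|---|---|
| Protocol Summary, Study Design | 24 h | 48 h |
| 6.1, schedule footnote | 24 h | 48 h |
| 7.1, last paragraph | 24 h | 48 h |
| 3.1 (twice) | 6 h | 48 h |
| 6.1.2.1 | 6 h | not given |
| 7.1, Patient scans | 6 h | not given |
| 12 | 6 h | 48 h |

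The maximum agrees wherever it is given; only the minimum conflicts.

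**Inputs**

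- Gap: 6 h = 360 min or 24 h = 1,440 min, from the sections above.
- If the 6 h ran from the end of a 90-min scan (the longest scan in section 3.1): 360 + 90 = 450 min between injections.
- Dose ratio A1/A2: 1 for equal doses. Section 7.1 allows ±10% around 2.5 MBq/kg, so the worst pair within tolerance is 1.1/0.9 = 1.22.
- 68Ga half-life T: assumed 60 to 75 min, with 68 min as a middle value. It is not in the documents.
- No biological clearance of the first dose beyond what applies to the second.

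**Formula**

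Residual as a share of the second dose = (A1/A2) × 2^(−gap/T). Both doses decay at the same rate, so this share holds throughout the second scan.

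**Results**

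| Gap between injections | A1/A2 | T = 60 | T = 68 | T = 75 |
|---|---|---|---|---|
| 360 min | 1 | 1.56% | 2.55% | 3.59% |
| 360 min | 1.22 | 1.91% | 3.12% | 4.39% |
| 450 min | 1 | 0.55% | 1.02% | 1.56% |
| 1,440 min | 1 | 0.000006% | 0.00004% | 0.00017% |

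For example, at T = 60 the 6 h gap is 360/60 = 6 half-lives, and 2^(−6) = 1.56%. The ±10% row is the first row times 1.1/0.9. Applying the same factor at 24 h gives at most 0.00017% × 1.22 = 0.0002%.

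**From whole-body activity to a region's SUV**

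The shift in a region is the residual times the ratio of late to early uptake there, which the documents do not give. For an assumed ratio of 0.5 to 1.5, equal doses and 6 h between injections, the range is 0.5 × 1.56 = 0.8% to 1.5 × 3.59 = 5.4%.

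**The case against.** The strongest reply is that the consequence is close to nil. The schedule describes separate-day visits, so same-day pairs may never occur. The carry-over remark in section 7.1 is a hedged practical expectation, made while discussing bladder activity, and a few per cent leaves it nearly true. Most of this stands. It limits the bias but does not resolve the conflict between sections.

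A second reply is that choosing 24 h presumes what the sponsor intended. Afternoon cyclotron shipments (section 7.11) and generator-first order (section 12) would fit morning-then-afternoon scanning. That is a fair inference but not something the protocol states. The recommendation of 24 h therefore rests on the existing schedule and on the decay figures, not on a claim about intent.

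Readers might also be tempted by stronger forms of the point:

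- **Larger residuals from unequal doses.** Section 3.3 has a clause beginning "If the amount of activity per kg body weight differs by more than 25% from the recommended dose of 2.5MBq/kg of body weight", but it triggers a longer acquisition and is not a dosing tolerance. The 100 and 300 MBq limits in the same section bound weight-based dosing across patients and do not describe one patient's two doses. Section 3.3 does say that activity will vary, so ±10% may sometimes be exceeded, but the documents give no wider tolerance to calculate with.
- **Confusion over the reference point.** Some sections count between scans and others between doses or injections. Section 7.1 starts PET with the bolus, so start-to-start and injection-to-injection are the same gap. Only counting from the end of the first scan differs, by up to 90 min, and that makes the residual smaller.

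**Conclusion.** The contradiction is in the current operative text, and no section resolves it. It is minor. If pairs are scanned at the 6 h limit, the second scan carries about 1.6 to 3.6% from the first at equal doses, up to 4.4% within the stated dose tolerance, and 0.6 to 1.6% if the 6 h runs from the end of a 90-min scan. So the carry-over statement in section 7.1 is not strictly true at the minimum gap set in the same paragraph, whereas at 24 h it holds for practical purposes.

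A reader might infer that carry-over threatens the equivalence conclusion. The figures do not support that: a one-directional shift of a few per cent is small against the 30% criterion in section 12 and unlikely to decide the result.

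The conflict between sections rests on the text alone. The size of the bias rests on the assumed half-life, on physical decay only, and on regional uptake that the documents do not report.

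**What to change.** In sections 3.1 (both places), 6.1.2.1, 7.1 (Patient scans) and 12, state one rule: at least 24 h and at most 48 h between injections. This matches the Protocol Summary, the schedule in section 6.1 and the end of section 7.1, and it makes the residual negligible.

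Add a sentence to section 12 for exceptions: if a pair is scanned at less than 24 h, record the injection-to-injection gap and both injected activities, and report the primary analysis with and without that pair.

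The cost is the text edits and the loss of same-day pairs. If the cyclotron product is first, as in section 3.1, and arrives in the afternoon, a scan 6 h later would fall at 18:00 or later, so little is lost. If the generator product is first, as in section 12, a same-day pair is easier to arrange and the loss is somewhat larger.
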